### 10.4.2 Sponsor Notification of Events

The Sponsor is responsible for reviewing all safety data to evaluate potential causality and anticipation of all ADEs, and shall conduct an expedited assessment of all SAEs, unanticipated ADEs, DDs that could have led to a SADE, including serious health threat.

The Sponsor is also responsible for reporting all reportable events according to the requirements and timelines of the regulatory authorities relevant to this clinical investigation. Country specific sponsor reporting responsibilities are outlined in the Sponsor's Safety Data Handling Plan.

The Safety Monitor for AE/DD assessment and any AE/DD related queries is:

Name Sponsor Safety Monitor:	
Country:	
Phone number:	
E-mail:	

### 10.5 Independent Data Monitoring Committee

An Independent Data Monitoring Committee (IDMC) will be established to provide an independent review of safety and compliance outcomes for this clinical investigation. The IDMC will review trial data and provide recommendations to the Sponsor regarding the course of the clinical investigation. The scope of the IDMC and its associated procedures will be outlined in the IDMC Charter.

## **11 DEVICE ACCOUNTABILITY**

Subject level device supply will be tracked using the Individual Subject Device Accountability Log Form (1295295).

As the device under investigation is cleared within current indications, device traceability from Sponsor to Site will be tracked through the commercial distribution process and the Sponsors local work instruction. Packing lists will be stored in the site files for reference.

Additionally, the Osia 2 system should be registered by the investigational site with the Sponsor according to the commercial registration practices as the devices remain with the subjects following the conclusion of the clinical investigation. If during the course of the trial, a repair or return is required, the investigational site and Sponsor will adhere to the commercial Return Material Authorization (RMA) process. Similarly, in the event a device requires explantation, the investigational site and the Sponsor will adhere to the commercial process in place for the return of explanted devices.

At the end of the clinical investigation, if the investigational site is in possession of any unused devices, all product should be returned to the Sponsor according to the commercial RMA process.

Further detail regarding device accountability tracking and storage will be detailed in the Monitoring Plan.

Contact information regarding the Osia 2 system is provided below.

Name of contact person of the Sponsor:	
Country and time zone:	
Phone number:	
Email:	

# **12 DEVIATIONS FROM THE CLINICAL INVESTIGATION PLAN**

The Investigator(s) must not deviate from the CIP, except in case of an emergency to protect the safety and well-being of the subject(s). Such deviations will be documented by the site personnel in the source documentation for the subject and reported to the relevant EC as per institutional requirements and to the Sponsor as soon as possible, but not later than 5 working days from the date of the emergency. Per 21 CFR 812.25(b) Sponsor is required to report emergency deviations to the FDA within 5 working days of notification of the event.

If there is a deviation from CIP-defined assessments or parts thereof are omitted or completed incorrectly, the deviation will also be documented by the site personnel in the source documentation for the subject. Depending on the type or severity of the deviation the Investigator may be required to notify the EC, particularly if the deviation potentially impacts subject safety, performance of [IMD][and/or comparator], or data integrity.

All CIP deviations will be documented in the eCRF to enable analysis and reporting by the Sponsor in the Clinical Investigation Report (CIR), or to the relevant regulatory authority(s), if applicable.

Gross misconduct on behalf of an Investigator, such as intentional non-compliance with CIP or GCP requirements or fraud, will result in disqualification of the Principal Investigator and/or Investigational Site from participation in the investigation. Data provided by the Principal Investigator or Investigational Site will be excluded from the per-protocol analysis group.

# **13 DATA MANAGEMENT**

The CRF will capture the datapoints necessary to determine the subject status according to the criteria described in section 6.3.

# 13.1 Source Data

An Origin of Source Data Form will be used to capture the location of source data kept at each site, outlining the individual site's process for certification.

Source data will be captured in clinic notes, paper-based source data worksheets, or printed directly from testing software. As indicated on the Origin of Source form, data collected may be entered directly into the eCRF which shall be considered source data for these items. If electronic medical records do not permit read only access for monitoring purposes, a certified printout must be provided, indicated by a dated signature by a member of the site team or generated through a validated process.

# **13.2** Methods for Data Entry and Collection

Data collection will be performed using **Constant and Second Second** for electronic data capture (EDC) on electronic Case Report Forms (eCRFs). Site staff will be trained on the completion of the eCRFs prior to obtaining access to the system and will have their own Login/Password. Access to clinical study information will be based on an individual's role and responsibilities.

uses role-based user permissions for data entry, viewing, and reporting options. All communications between users and the EDC server are encrypted. Web servers are protected by a managed firewall. This application is designed to be in compliance with applicable regulations including 21 CFR Part 11.

The application will include programmed data consistency checks and supports manual generation of data clarifications/queries, including documentation of site responses. This application maintains a comprehensive audit trail for all data entered, including updates and queries, and documents the time that each entry occurred and who made the entry.

Principal Investigators will affirm that the data for each subject at their site is accurate and complete by way of an electronic signature.

In addition, de-identified electronically generated data will be collected from the Osia Fitting Software. The unamended data file shall be regarded as the source.

# 13.3 Database Lock

The database will be locked upon the completion of collection of data from Visit 4 6-months and again at the completion of the study.

The process for database lock is described in the Data Management Plan.

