### 6.2.5 Recruitment and Study Duration

The following subject status definitions apply:

- Enrolled: A subject who has a signed Informed Consent form for the study.
- Screened: A subject who has a signed Informed Consent form and has met the eligibility criteria.
- Screen Fail: An enrolled subject who has been determined to not meet one or more eligibility criteria.
- Participated: An enrolled subject who has met eligibility criteria and has been treated with the Osia 2 System.
- Discontinued: An Enrolled subject who withdrew consent, was discontinued by the Investigator or Sponsor before the expected End of Study visit or was lost to follow-up. Discontinued subjects may still have safety follow-up data collection until their scheduled End of Study visit, for reasons described in section 6.2.6.
- Completed: Enrolled subjects who complete the required treatment and visit schedule.

The recruitment period for the clinical investigation is estimated to be 12 months from the time of first subject consent to recruitment of the last subject.

The expected duration of each subject's participation in the clinical investigation, is anticipated to be 14 to 18 months from the time of informed consent to End of Study Visit 5.

Clinical Investigation completion is last subject last visit. AE recording will continue for each subject until completion of their End of Study visit. Ongoing SAEs and SADEs will be followed for an additional 30 days, or until resolution or stabilization within the 30-day period following End of Study. Management of the SAE/SADE beyond clinical investigation completion will be absorbed into standard clinical and medical care by the participating clinical investigational site.

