### 8.2 Endpoints

### 8.2.1 Primary Endpoint

The primary endpoint is adverse events and serious adverse events Surgery through Visit 4 (6 Months). Events will be summarized by type, frequency, and severity.

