## 10.2 Recording and Handling of Adverse Events

Subjects shall be carefully monitored during the clinical investigation and the investigator should enquire about AEs at investigation visits.

All AEs will be recorded from the time of implantation. AE recording will continue for each subject until completion of their End of Study visit. Ongoing SAEs and SADEs will be followed for an additional 30 days, or until resolution or stabilization of the event, whichever comes first. Management of the SAE/SADE beyond clinical investigation completion will be absorbed into standard clinical and medical care by the participating clinical investigational site.

Source notes should indicate the evaluation for AEs, even if there was none to report. All required AEs will be reported if observed, even if anticipated and/or acknowledged as a risk factor in the consent.

All AEs will have the following information documented: start and stop dates, action taken, outcome, severity and investigators opinion on the potential relationship to the Osia 2 system and study procedures. If an AE changes in severity, the most severe (highest) grade will be captured for that event on the Adverse Events CRF.

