#### 5.6.1 Primary Endpoint

The primary endpoint is device and procedure related adverse events Surgery through Visit 4 (6 Months). Events will be summarized by type, frequency, and severity.

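### The 6-month severity table can carry grades reached after Visit 4, and the final lock, read literally, can precede the end of required SAE follow-up

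*Protocol*

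**What the plan says.** **Locks.** Protocol 13.3 sets two: "The database will be locked upon the completion of collection of data from Visit 4 6-months and again at the completion of the study". It adds: "The process for database lock is described in the Data Management Plan". That plan is not among the documents.

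**Severity.** The primary endpoint (protocol 8.2.1, SAP 5.6.1) runs from surgery to Visit 4 at 6 months and is summarised by type, frequency and severity. The protocol counts all AEs and SAEs and the SAP only device- and procedure-related ones, but the window is the same in both. Under protocol 10.2, AEs are recorded from implantation to the End of Study visit (Visit 5, 12 months), and "If an AE changes in severity, the most severe (highest) grade will be captured for that event on the Adverse Events CRF". The AE items listed there include start and stop dates for the event but no date for the grade.

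**Completion and SAE follow-up.** Protocol 6.2.5 states: "Clinical Investigation completion is last subject last visit". The same section states: "Ongoing SAEs and SADEs will be followed for an additional 30 days", with an earlier end on resolution or stabilisation. Sections 6.3.3 and 10.2 repeat the requirement.

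**Use of the first lock.** Regulatory submission follows the 6-month data, and 12-month data are supplemental (protocol 8.8, SAP 5.10).

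**The concern.** Severity has a 6-month window, but the form stores a single undated grade that can be raised until month 12. The first lock comes when the last child has had Visit 4, and by then children enrolled earlier have had up to six further months in which an open event can be upgraded. Take two children with the same event, mild at month 5 and severe at month 10. The early-enrolled child can appear as severe in the 6-month table, and the late-enrolled child as mild. The start date screens out events that begin after Visit 4, but it cannot restore an earlier grade. The primary endpoint has no hypothesis test, so this descriptive table is itself part of the result.

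The second lock raises a separate question of completeness. If it falls on last subject last visit, outcomes of SAEs or SADEs still open in the last children could be collected after the database has closed.

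**Working it through.** The plan gives no figure for either effect. Its precision figures for 50 subjects reproduce and are not in question: t(0.975, 49)/√50 = 0.2842 (stated 0.284), and the chance of at least one event at a 5.9% rate is 1 − 0.941^50 = 0.952 (stated above 95%).

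**Is there a rule that fixes the grade at Visit 4?**
- SAP 5.6.1.1 uses observed events without imputation and gives no cut-off.
- SAP 5.1.2 assigns visit-based assessments to nominal visits, which does not cover AEs.
- SAP 5.8 defines rates by analysis interval and does not mention severity.
- The SAP was written against protocol version 3.0. The protocol's change history places the addition of lock procedures in version 4.

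Neither document gives a per-child AE cut-off or a rule for severity at Visit 4.

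**Exposure at the first lock.** Inputs: 50 children and 12 months' recruitment (protocol 6.2.5), with AE recording to month 12. Assumption: surgeries evenly spread.
- The first lock is at 12 + 6 = 18 months. A child operated on U months before the last surgery has min(U, 6) months of recording after Visit 4.
- With U uniform on 0 to 12, the mean is (18 + 36)/12 = 4.5 months, and half the children have reached month 12.
- With 50 evenly spaced surgeries, 49 are past Visit 4, 25 have reached Visit 5, and about 223 person-months after Visit 4 sit beside 50 × 6 = 300 in the window. For accrual over 6 to 18 months, the 223 becomes 150 to 248.

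**Events re-graded.** Only an event with onset by Visit 4, still open then and worsening before the lock, is affected. The documents give no rate, so these ranges are assumed:

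| Open events at Visit 4 | Chance of worsening | Expected re-graded |
|---|---|---|
| 2 to 10 | 5% to 20% by the first lock | 2 × 0.05 = 0.1 to 10 × 0.20 = 2 |
| 5 to 15 | 10% to 30% by month 12, times 4.5/6 = 0.75 | 0.4 to 3.4 |
| 5 to 15 | same, but noted only at Visit 5, times 0.50 | 0.25 to 2.25 |

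The third row reflects that no visit is scheduled between months 6 and 12. In the first row, the chance of at least one re-graded event runs from 1 − 0.95² = 10% to 1 − 0.8^10 = 89%.

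**Final lock.** Children whose Visit 5 falls in the 30 days before last subject last visit: 50 × 30/365 = 4.1. Counting evenly spaced surgeries gives 5, and 9 down to 3 for accrual of 6 to 18 months. Only an SAE or SADE still open at End of Study in one of these children could be caught.

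**The case against.** **The grade at Visit 4 may be recoverable.** AEs are reviewed at every visit, source notes record each evaluation, the EDC system time-stamps every entry and update (protocol 13.2), and the Data Management Plan may set a cut-off. This stands against a stronger inference that a reader might draw, namely that the table will contain later grades and that the earlier ones are lost. The documents support only that it can. But the audit trail dates data entry, not clinical worsening. It helps only if the lower grade was entered first, and neither document tells the analyst to use it.

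**There may be no conflict.** The endpoint can be read as events with onset in the window, each carrying its form grade, which is by definition the highest. Any error then overstates severity, which is conservative for safety. That is a legitimate choice, but it is not stated. Even on that reading, at the first lock the grade is a maximum over a period that differs between children by up to six months, according to enrolment date.

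**The effect is small.** This stands. Event counts, types and the percentage of children with an event do not change. The site and subgroup models (SAP 5.7, 5.9) use proportions of children, not severity, and there is no success threshold. The earlier paediatric study in protocol 3.2.2.2 had 15 AEs in 14 subjects, all resolved by closure, and one SAE. At that SAE rate, four children would have 4 × 1/14 ≈ 0.3 SAEs over the whole study, and fewer still open at month 12.

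**The lock wording is loose.** Section 13.3 names no day and defers the process elsewhere. That is fair as to what will happen in practice, but with the definition in 6.2.5 the literal gap remains.

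**Conclusion.** Both points hold as gaps between stated rules, and both are modest.

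(a) For events with onset by Visit 4 that are still open then, the 6-month severity table can carry a grade reached later, depending on how early the child was enrolled. Probably about 0 to 3 events are involved. That range rests on assumed numbers of open events, assumed chances of worsening and, where the 0.75 or 0.50 factor is used, even accrual. It would be wrong to infer from the 4.5-month mean that the whole primary endpoint describes 10.5 months of follow-up; that extra time matters only for open events that worsen. Nor do the documents say that the 6-month table will be re-run at the final lock.

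(b) Read literally, the final lock can precede follow-up that the protocol requires. This is limited to SAEs or SADEs ongoing at End of Study in roughly 4 of 50 children, assuming even 12-month accrual, and 30 days is the maximum. The documents do not show that outcomes will be missing, and the 6-month primary analysis is not affected.

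**What to change.** (a) Add one item to the AE form: for AEs ongoing at Visit 4, the highest grade reached up to Visit 4. Add one SAP sentence saying that the primary severity table uses this grade and that the overall maximum is kept for the supplemental 12-month table. It is best captured prospectively, since later reconstruction depends on what was entered and when.

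(b) Reconcile protocol 13.3 with 6.2.5 and 10.2 so that the final lock follows last subject last visit plus completion of the SAE/SADE follow-up already required.

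The cost is the form item, the SAP sentence and a final lock up to 30 days later. Submission rests on the first lock and is not delayed. Sample size, power and alpha do not change.

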# **14 CONFIDENTIALITY**

The investigator and site staff will collect and process personal data of the subjects in accordance with governing data privacy regulations, including Good Clinical Practices (GCPs) and with the Health Insurance Portability and Accountability Act of 1996 (HIPAA).

Data will be reported to the Sponsor on CRFs or related documents (for example, questionnaires). Subjects will be identified on CRFs and other related documents only by a unique subject identification code and shall not include the subject's name or other personal identifiable information. Completed CRFs or related documents are confidential and will only be available to the Investigator and site staff, the Sponsor and their representatives, and if requested to the Ethics Committee and national regulatory authorities. Publications or submission to a regulatory authority shall not disclose the identity of any subject.

# **15 ETHICS COMMITTEE AND REGULATORY AUTHORITY APPROVAL**

The clinical investigation will not commence prior to the written favourable opinion or approval from the EC and regulatory authority is obtained.

The final Sponsor-approved version of the CIP, Informed Consent Form, and other necessary documents shall be submitted to the EC. A copy of the EC opinion/approval shall be provided to the Sponsor.

The Investigator shall forward to the Sponsor, for review and approval, any amendment made to the approved ICF and any other written information to be provided to the subject prior to submission to the EC.

The Sponsor and Principal Investigator will continue communications with the EC, as required by national regulations, the clinical investigational plan, or the responsible regulatory authority.

Any additional requirements imposed by the EC or regulatory authority will be implemented by the Sponsor.

The Investigator shall submit the appropriate documentation if any extension or renewal of the EC approval is required. In particular, substantial amendments to the CIP, the ICF, or other written information provided to subjects will be approved in writing by the EC.

The Investigator shall report to the EC any new information that may affect the safety of the subjects or the conduct of the clinical investigation. The Investigator will send written status summaries of the investigation to the EC regularly, as per local EC requirements.

Upon completion of the clinical investigation, the Investigator shall provide the EC with a brief report of the outcome of the clinical investigation, as per local EC requirements.

The clinical investigation is covered by clinical trial insurance, meeting the requirements of the participating countries.

# **16 SUSPENSION OR PREMATURE TERMINATION**

The Sponsor will discontinue the clinical investigation site if:

- 1) major non-adherence to the CIP or GCP principles is occurring
- 2) it is anticipated that the subject recruitment will not be adequate to meet the objectives of the clinical investigation

An ongoing clinical investigation may be discontinued in case of:

- 1) device failure
- 2) serious or intolerable ADE, leading to the explant or discontinued use of the device
- 3) subject's death

In the event of premature study termination, the subjects will continue to be managed clinically by their medical provider.

## **17** AMENDMENTS TO THE CLINICAL INVESTIGATION PLAN

Sponsor will notify all site Principal Investigators of changes to the CIP. No changes in the CIP or investigation procedures shall be made without mutual agreement of the Principal Investigator and the Sponsor. This agreement will be documented as a CIP amendment. Amendments will require notification to the Ethics Committees (ECs) by the Principal Investigators and to the relevant regulatory authority(s) by the Sponsor.

## **18 RECORD KEEPING AND RETENTION**

Data generated from the clinical investigation will be stored in a limited-access file area and be accessible only to representatives of the study site, the Sponsor and its representatives, and relevant health authorities/regulatory agencies. All reports and communications relating to study subjects will identify subjects only by subject unique identification code. Complete subject identification will be maintained by the Investigator. This information will be treated with strict adherence to professional standards of confidentiality.

Per 21 CFR 812.140 (d), an investigator or sponsor shall maintain the records required by this subpart during the investigation and for a period of 2 years after the latter of the following two dates: The date on which the investigation is terminated or completed, OR the date that the records are no longer required for purposes of supporting a premarket approval application, a notice of completion of a product development protocol, a humanitarian device exemption application, a premarket notification submission, or a request for De Novo classification.

The Sponsor will notify the Principal Investigator when records are no longer needed. The Investigator will not discard any records without notifying the Sponsor. If the Principal Investigator moves from the current investigational site, the Sponsor should be notified of the name of the person who will assume responsibility for maintenance of the records at the investigational site or the new address at which the records will be stored. The Investigator will notify the Sponsor as soon as possible in the event of accidental loss or destruction of any study documentation.

